## 10.3 Statistical Analyses

The SAP will be developed and finalized before database lock and will describe the selection of participants to be included in the analyses, and procedures for accounting for missing, unused, and spurious data. Below is a summary of planned statistical analyses of the primary and secondary endpoints.

[figure not shown]

[figure not shown]
### 10.3.1 Efficacy Analyses

Endpoint	Statistical Analysis Methods
Primary	
The primary endpoint, PFS based on investigator assessment, will be compared in two randomized arms via a two-sided, log-rank test stratified by the same factors used in randomization. Participants who die without a reported progression will be considered to have progressed on the date of their death. Participants who did not progress or die will be censored on the date of their last tumor assessment. Participants who did not have any on study assessments and did not die will be censored on the randomization date. A participant who initiates a subsequent anti-cancer therapy will be censored on the date of last tumor assessment prior or on the start date of their subsequent anti-cancer therapy. Sensitivity analyses will be performed using different PFS definitions to assess the robustness of the primary analysis. The PFS curve, median and PFS rate at 6, 12, 18, and 24 months for each randomized arm will be estimated using the Kaplan-Meier product-limit method. Two sided, 95% confidence intervals for median PFS will be computed by Brookmeyer and Crowley method. A two-sided, 95% confidence interval for the PFS rates will be computed by Greenwood method. The hazard ratio (HR) and corresponding two-sided <math>100 * (1-\alpha)\%</math> (<math>\alpha</math> adjusted for the interim analysis) confidence interval will be estimated in a Cox proportional hazards model using randomized arm as a single covariate, stratified by the same factors used in randomization.

Secondary	
CRR/CMR based on investigator assessment will be compared in two randomized arms via a two-sided, Cochran-Mantel-Haenszel test stratified by the same factors used in randomization. An estimate of the treatment odds ratio between the nivolumab + BV and BV arm along with corresponding two-sided 95% CIs and p-value will be presented. The estimate of the CRR/CMR and associated exact two-sided 95% CIs (by Clopper - Pearson method) will be presented for both arms.
 
ORR as defined as proportion of participants who achieved CR/CMR or PR/PMR before taking any subsequent anti-cancer therapy, will be computed in each treatment group along with the exact 95% CI using Clopper-Pearson method.
 
Duration of response (or complete response) in each treatment group will be estimated using KM product-limit method for participants who achieve PR or CR /CMR (or CR/CMR only). Median values along with two-sided 95% CI will be calculated.
 
The OS curves for each treatment group will be estimated using the Kaplan-Meier product-limit method. Two-sided, 95% confidence intervals for median OS will be provided. For participants without documentation of death, OS will be censored on the last date the participant was known to be alive. When the primary endpoint, PFS, is statistically significant, the secondary endpoint CRR/CMR will be tested. The hierarchical testing procedure that ensures the study-wise type I error is controlled at 5% levels will be described in the SAP.

### 10.3.2 Safety Analyses

Safety analyses will be performed in all treated participants. Descriptive statistics of safety will be presented using NCI CTCAE version 4.03. All on-study AEs, treatment-related, AEs, SAEs and treatment-related SAEs will be tabulated using worst grade per NCI CTCAE v4.03 criteria by system organ class and MedDRA preferred term. On-study lab parameters including hematology, chemistry, liver function, thyroid function, and renal function will be summarized using worst grade per NCI CTCAE v4.03 criteria.

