**Table 2-3: Procedural Outline after the Treatment Period (CA209812) - Follow Up**

Procedure	X, Follow-Up, Visits 1 and 2 a	Notes
Safety Assessments		
Targeted Physical Examination	X	Lymph node areas (for example, but not limited to, submandibular, cervical, supraclavicular, axillary, or inguinal lymph node), and abdominal organs (eg, spleen, liver)
Serious Adverse Events Assessment	X	SAEs related to any later protocol-specified procedure must be collected
Adverse Events Assessment	X	Non-serious AEs and SAEs must be collected up to 100 days after study treatment discontinuation.
Peripheral Neuropathy	X	Any AEs of peripheral neuropathy must be followed until resolution or end of study, whichever occurs first.
Monitoring for (in)fertility	X	Completion of CRF through Safety Follow-up Visit 2.
Monitoring for cardiotoxicity and pulmonary toxicities	X	Completion of CRF through Safety Follow-up Visit 2 and work up as indicated (for clinical symptoms)
Monitoring for secondary neoplasms	X	Completion of CRF through Safety Follow-up Visit 2.
Laboratory Tests	X	During Follow-up visit 1 and Follow-up visit 2: CBC with differential, BUN or serum urea level, serum creatinine, sodium, potassium, calcium, magnesium, chloride, glucose, AST, ALT, total bilirubin, alkaline phosphatase, LDH.
Thyroid Function Testing	X	TSH (reflex to free T3 and free T4 if abnormal result) Every 9 weeks
Pregnancy Test (WOCBP only)	X	Serum or urine (WOCBP only)

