**Figure 5.1-1: Study Design Schematic**

Abbreviations: BV = brentuximab vedotin; PFS = progression-free survival; CRR = complete response rate; OS overall survival; ORR = objective response rate; DOCR = duration of complete response; DOR = duration of response.

This is a 1:1 randomized, open-label Phase 3 study in advanced cHL participants ≥ 18 years old who are relapsed refractory or ineligible for ASCT. Patients will be balanced in the 2 groups in regards to prior therapies. Approximately 340 participants will be treated in one of 2 arms. In one arm, participants will receive nivolumab 360 mg IV every 3 weeks until progression or unacceptable toxicity (except for patients in CR who can discontinue at 2 years) plus BV 1.8 mg/kg IV every 3 weeks for up to 16 cycles, or until disease progression or unacceptable toxicity,

whichever occurs first. In the other arm, participants will receive BV alone 1.8 mg/kg every 3 weeks for up to 16 cycles, disease progression, or unacceptable toxicity, whichever occurs first. Discontinuation of study therapy can also occur if the participant meets other criteria outlined in [Section 8.1](#). Participants receiving nivolumab who achieve CR may discontinue treatment after a maximum of 2 years of therapy, provided that there is no prohibitive toxicity. Participants can be brentuximab vedotin-naïve, or can have prior BV treatment as a single agent or in combination in any line of therapy. Randomization stratification will be performed on the following two factors: 1) Prior ASCT status (YES/NO). 2) Prior BV use (YES/NO). Participants will be balanced based on the stratification factors per arm. The two arms will be balanced in regards to these stratification factors.

Participants will undergo screening evaluations to determine eligibility within 28 days prior to first dose. Each 21-day dosing period will constitute a cycle.

Study visits and endpoint measurements will occur as indicated in [Table 2-1](#) through [Table 2-3](#).

Any participant who discontinues the study treatment prior to progression will be followed for progression, then survival, in the follow up phase of the study.

- No dose reductions or escalations of nivolumab are permitted. Skipped doses will not be made up. For dose modifications or reductions of BV, see [Section 7.4.2](#).

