## 7.1 Treatments Administered

Infusions will be performed over a period of once every 3 weeks. Participants should begin study treatment within 3 calendar days of randomization. Participants will be monitored continuously for AEs while on study. Study treatment modifications (eg, dose delay or discontinuation) will be based on specific laboratory and AE criteria (Section 7.4). Doses of study treatment may be interrupted, withheld, or discontinued depending on how well the participant tolerates the study treatment. Treatment with nivolumab will be continued as described in Section 5.1 until disease progression or unacceptable toxicity. Participants treated with nivolumab who achieve a CR may discontinue treatment after a maximum of 2 years of therapy, provided that there is no prohibitive toxicity. Administration of BV should be discontinued after a maximum of 16 cycles, or until disease progression or unacceptable toxicity, whichever occurs first.

All participants who discontinue therapy will be followed through Safety Follow-up Visit 2.

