## **9.2 Adverse Events**

The definitions of an AE or serious adverse event (SAE) can be found in [Appendix 3](#).

AEs will be reported by the participant (or, when appropriate, by a caregiver, surrogate, or the participant's legally authorized representative).

The investigator and any designees are responsible for detecting, documenting, and reporting events that meet the definition of an AE or SAE and remain responsible for following up AEs that are serious, considered related to the study treatment or the study, or that caused the participant to discontinue before completing the study.

All SAEs must be collected that occur during the screening period and within 100 days of the last dose of nivolumab. For participants randomized/assigned to treatment and never treated with study treatment, SAEs should be collected for 30 days from the date of randomization.

All nonserious adverse events (not only those deemed to be treatment related) should be collected continuously during the treatment period and for a minimum of 100 days following discontinuation of study treatment.

In the present study, AEs, treatment-related AEs, SAEs, and treatment-related SAEs occurring > 100 days after the last study treatment administration during the long-term follow-up periods will be recorded on the eCRF and will be tabulated for AEs of special interest for immuno-oncology agents and for BV. Effects on long-term fertility and evolution of secondary neoplasms will be assessed.

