4.2.3 Safety and Tolerability

Safety will be analyzed through the incidence of deaths, adverse events, serious adverse events, adverse events leading to discontinuation, adverse events leading to dose delay, select adverse events and specific laboratory abnormalities (worst grade) in each treatment group. Toxicities will be graded using the National Cancer Institute (NCI) Common Terminology Criteria for Adverse Events (CTCAE) version 4.0. See details in the Core Safety SAP.

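### Crude by-arm AE incidence and worst-grade tables compare unequal observation time, because safety capture follows the last dose and only BV is capped; neither document names an exposure-adjusted summary

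*Protocol*

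**What the plan says.** **Summaries.** Protocol 10.3.2: "All on-study AEs, treatment-related, AEs, SAEs and treatment-related SAEs will be tabulated using worst grade". On-study laboratory values are also summarised by worst grade. SAP 4.2.3: "Safety will be analyzed through the incidence of deaths, adverse events, serious adverse events, adverse events leading to discontinuation", by treatment group, with detail left to the Core Safety SAP. Neither place mentions person-time or a common observation window.

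**Treatment length.** Protocol 5.1 gives the control arm "BV alone 1.8 mg/kg every 3 weeks for up to 16 cycles, disease progression, or unacceptable toxicity, whichever occurs first", and "Each 21-day dosing period will constitute a cycle". Protocol 7.1 repeats the limit: "Administration of BV should be discontinued after a maximum of 16 cycles". The combination arm receives "nivolumab 360 mg IV every 3 weeks until progression or unacceptable toxicity (except for patients in CR who can discontinue at 2 years"; nivolumab has no cycle limit.

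**Capture.** Protocol Table 2-3: "Non-serious AEs and SAEs must be collected up to 100 days after study treatment discontinuation". Laboratory tests accompany each dose (Table 2-2) and then occur at Follow-up Visits 1 and 2 (Table 2-3). Visit 2 is 100 ± 7 days after the last dose, and Protocol 5.3 ends the trial there.

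**Statements that do not agree.** Protocol 9.2 says non-serious AEs "should be collected continuously during the treatment period and for a minimum of 100 days following discontinuation of study treatment", which makes 100 days a floor. It also says that AEs and SAEs beyond 100 days will be recorded, and tabulated for AEs of special interest. It counts the SAE window from the last nivolumab dose; Protocol 9.2.1 counts it from the last dose of study treatment.

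**The concern.** A participant's chance of appearing in a crude AE table, and the worst of a series of laboratory grades, both rise with time under observation. Here that time is set by treatment duration, which differs between arms by design. After cycle 16, a BV-alone participant has two follow-up visits left. A combination participant who has not progressed still attends every three weeks for AE assessment and blood tests.

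An excess in the combination column could then reflect toxicity, longer ascertainment or both, and the table alone would not say which. If the combination also delays progression, the gap in observation widens, so better disease control makes the crude safety column look worse. Enrollment stopped at 23 participants, so by-arm safety is one of the few outputs that readers will still use.

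**Working it through.** **1. The plan's own figure.** Protocol 5.5.1 describes 16 BV cycles as roughly one year. 16 × 21 = 336 days; 336 / 30.4375 = 11.0 months, or 336 / 365.25 = 0.92 year. It reproduces. (30.4375 days per month is the conversion in SAP section 8.)

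**2. Maximum windows.**
- BV alone, no delays: dose 16 falls 15 × 21 = 315 days after dose 1. (315 + 100) / 30.4375 = 13.6 months. With the 7-day visit allowance it is 422 / 30.4375 = 13.9. Assumed cumulative delays of 3 or 6 weeks give 436 / 30.4375 = 14.3 or 457 / 30.4375 = 15.0 months.
- Nivolumab stopped at 2 years: 24 + 100 / 30.4375 = 24 + 3.29 = 27.3 months, a ratio of 2.0. Without that optional stop there is no fixed limit.

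**3. Mean windows.** These are maxima; most participants stop earlier. Assumptions:
- exponential PFS, with stopping only at progression or at the cap;
- BV median PFS of 5.6 or 9.3 months (the two reports of the phase 2 study in Protocol 3.2);
- nivolumab to 24 months;
- PFS hazard ratio (HR) 1 or 0.62. The design HR is not visible. 0.62 is back-solved from 187 events at 90% power: exp(−2 × (1.960 + 1.282) / √187) = 0.62.

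Mean window = (1 − e^(−λc)) / λ + 3.29, where λ = HR × ln 2 / median and c is the cap: 315 / 30.4375 = 10.35 months for BV, 24 for nivolumab. For BV at median 5.6, λ = 0.1238 and e^(−λc) = 0.278, so the mean is 0.722 / 0.1238 + 3.29 = 9.1 months.

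| BV median | BV alone | Combination, HR 1 | Combination, HR 0.62 |
|---|---|---|---|
| 5.6 | 9.1 | 11.0 | 14.3 |
| 9.3 | 10.5 | 14.5 | 17.8 |

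On the same assumptions, 28% (median 5.6) to 46% (median 9.3) of BV-alone participants reach dose 16.

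**4. Crude incidence with the same AE hazard h in both arms.** Incidence = 1 − e^(−3.29h) × [λ/(λ+h) × (1 − e^(−(λ+h)c)) + e^(−(λ+h)c)]. For BV alone at median 5.6 and h = 0.05: 1 − 0.8485 × [0.7123 × 0.8345 + 0.1655] = 35.5%.

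| h per month | BV median | BV alone | Combination, HR 1 (excess) | Combination, HR 0.62 (excess) |
|---|---|---|---|---|
| 0.02 | 5.6 | 16.4% | 19.0% (2.5) | 23.8% (7.4) |
| 0.02 | 9.3 | 18.7% | 24.1% (5.4) | 28.9% (10.2) |
| 0.05 | 5.6 | 35.5% | 39.2% (3.7) | 47.0% (11.5) |
| 0.05 | 9.3 | 39.8% | 47.5% (7.7) | 54.9% (15.0) |

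The HR 1 column comes from the difference in caps alone.

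**5. Front-loaded hazard.** With an assumed 0.15 per month for 3 months and 0.01 thereafter, the excess falls to about 1 to 4 points across the same scenarios.

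**6. Would a plain 48-week cut equalise time?** No. A participant whose last dose falls before day 336 − 100 = 236 (7.75 months) loses scheduled coverage before week 48. Under the step 3 assumptions that is 44% to 62% of BV alone, against 30% to 45% of the combination at HR 0.62.

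**The case against.** **The controlling document is not available.** The SAP leaves safety methods and study periods to the Core Safety SAP, and its section 7.6 is almost entirely cross-references. What counts as on-study in the tables is therefore not visible. This stands. A reader might infer that no exposure adjustment is planned; the documents support only that neither of them names one.

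**Capture does not simply stop at day 100.** A reader might infer that BV-alone participants have no safety coverage after 13.6 months. Protocol 9.2 makes 100 days a minimum and provides for later events, Table 2-3 follows neuropathy to resolution or end of study, 9.4 follows laboratory toxicities until they resolve or are judged irreversible, and 9.2.1 requires later related SAEs to be reported. So that reading is too strong. What remains is that scheduled contact ends at Follow-up Visit 2 and the later-event provision has no visit in which to operate. The 13.6 months also assumes no BV delays, which Protocol 7.4.2 permits.

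**Exposure is already reported.** SAP 7.4.1 plans Kaplan-Meier treatment duration, cycles and cumulative dose by arm. A reader can set these beside the AE table. That helps, but it gives neither a rate nor person-time at risk.

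**The size is assumed.** No AE hazard is given in the documents, the HR of 0.62 is inferred, and the BV medians come from a post-ASCT cohort, whereas this trial also admits ASCT-ineligible and previously BV-treated participants. With 23 / 2 = 11.5 per arm, 2.5 to 15 points is 0.3 to 1.7 people, against a standard error of about √(2 × 0.4 × 0.6 / 11.5) = 20 points at 40% incidence. All of this stands.

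**Crude incidence answers a fair question.** Nivolumab until progression is the assigned regimen, and cumulative incidence over the regimen as given is a legitimate description. So the crude tables are not an error; they are incomplete for comparing arms.

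**Conclusion.** The point holds as a cheap improvement. The named by-arm tables compare unequal observation time, and they do so even with equal PFS, because BV is capped and nivolumab is not. The calendar figures (13.6 months without delays; 27.3 months for a 2-year nivolumab stop) follow directly from the documents.

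The incidence excess of about 2.5 to 8 points at HR 1, and 7 to 15 points at HR 0.62, is an illustration. It rests on a constant and equal AE hazard, exponential PFS and a back-solved HR. It should not be read as an estimate of bias in this trial: an early-onset hazard gives about 1 to 4 points, and the sample is far too small to detect either. The consequence is for how a descriptive table is read, since Protocol section 10 excludes formal testing.

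Separately, Protocol Table 2-3 and sections 5.3, 9.2 and 9.2.1 disagree on the post-treatment AE and SAE window. The 9.2 SAE window is undefined for participants who never receive nivolumab.

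**What to change.** - Keep the crude tables in Protocol 10.3.2 and SAP 4.2.3. Beside them report, by arm, total person-time at risk (first dose to last dose + 100 days) and exposure-adjusted incidence for AEs, SAEs, Grade 3-4 AEs and select AEs. If the Core Safety SAP already specifies this, cite the section in SAP 7.6 instead.
- Optionally add an early common-window summary based on time to first event, censored at the end of each participant's capture window, because a plain 48-week cut leaves coverage unequal. Read it beside the crude tables, not in place of them, so that late events on continuing nivolumab stay visible.
- Reconcile Protocol Table 2-3 and sections 5.3, 9.2 and 9.2.1 so that one post-treatment AE and SAE window is stated and is defined for both arms.

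Cost: some wording and a few tables. No new data are needed; SAP 7.3.1 already lists first and last dose dates. The rates will be imprecise at about 12 per arm, and they assume a roughly constant hazard, which should be stated with them.

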#### **10.3.4 Interim Analyses**

[figure not shown]
As described in [Section 10.1](#), an interim analysis of PFS assessed by BICR was to be performed after at least 131 PFS events (70% of total PFS events needed for final analysis) had occurred. It also required a minimum follow up of 6 months from the last patient first visit. This analysis was to be reviewed by the DMC while the Sponsor remained blinded. The estimated timing of this analysis was to be around 40 months after the start of randomization. The SAP will further describe the planned interim analyses.

[figure not shown]

## 12 APPENDICES

**APPENDIX 1 ABBREVIATIONS AND TRADEMARKS**

Term	Definition
ADC	anti-drug conjugate
AE	adverse event
AIDS	Acquired Immuno-Deficiency Syndrome
ALP	alkaline phosphatase
ALT	alanine aminotransferase
ASCT	autologous stem cell transplant
AST	aspartate aminotransferase
BICR	Blinded Independent Central Review
BMS	Bristol-Myers Squibb
BOR	best overall response
BP	blood pressure
BUN	blood urea nitrogen
BV	Brentuximab Vedotin
C	Celsius
Ca	calcium
Cavgss	average steady state concentration
CFR	Code of Federal Regulations
cHL	classical Hodgkin lymphoma
CI	confidence interval
Cl	chloride
CL	clearance
CLss	steady state clearance
Cmaxss	maximum concentration at steady state
Cminss	minimum concentration at steady state
CMR	complete metabolic response
CMV	cytomegalovirus
CR	complete response (remission)
CRF	case report form, paper or electronic

Term	Definition
CrCL	creatinine clearance
CRR	complete response rate
CT	computed tomography
CTLA	cytotoxic T-lymphocyte associated (protein)
CV	coefficient of variation
DILI	drug-induced liver injury
dL	deci-liter
DLCO	Diffusing capacity of the lung for carbon monoxide
DSMC	Data Safety Monitoring Committee
DOCR	duration of complete response
DOR	duration of response
ECG	electrocardiogram
ECOG	Eastern Cooperative Oncology Group
eCRF	electronic case report form
eg	exempli gratia (for example)
ELISA	enzyme-linked immunosorbent assay
EOI	end of infusion
EOT	end of treatment
FDA	Food and Drug Administration
FDG	fluorodeoxyglucose
FFPE	formalin-fixed paraffin-embedded
FSH	follicle stimulating hormone
FU	Follow-up
g	gram
G-CSF	granulocyte colony stimulating factor

Term	Definition
GFR	glomerular filtration rate
GM-CSF	granulocyte macrophage colony stimulating factor
h	hour
HBV	hepatitis B virus
HBV sAG	hepatitis B virus surface antigen
HCV	hepatitis C virus
Hep B 	hepatitis B
HIPAA	Health Insurance Portability and Accountability Act
HIV	Human Immunodeficiency Virus
HL	Hodgkin lymphoma
HR	hazard ratio
HRT	hormone replacement therapy
IB	Investigator's Brochure
ICD	immunogenic cell death
ICH	International Council on Harmonisation
ICOS	Inducible T-cell Costimulator
ie	id est (that is)
IEC	Independent Ethics Committee
IFN	interferon
IHC	immunohistochemistry
IMP/IP	investigational medicinal product / investigational product
I-O	Immuno-oncology
IPS	International Prognostic Score
IRB	Institutional Review Board
IRT	Interactive Response Technology
IU	International Unit
IUD	intrauterine device
IV	intravenous

Term	Definition
K	potassium
kg	kilogram
L	liter
LDH	lactate dehydrogenase
LDi	longest diameter
mg	milligram
Mg	magnesium
min	minute
mL	milliliter
MMAE	monomethyl auristatin E
MRI	magnetic resonance imaging
MST	medical safety team
MTD	Maximum Tolerated Dose
N	number of subjects or observations
Na	sodium
NCI	National Cancer Institute
NE	not evaluable
NSCLC	non-small cell lung cancer
ORR	objective response rate
OS	overall survival
PD-1	programmed death 1 (receptor)
PD-L1/PD-L2	programmed death ligand 1/2
PET	positron emission tomography
PFS	progression-free survival
PFT	pulmonary function test
PK	pharmacokinetics
PMD	progressive metabolic disease
PML	progressive multifocal leukoencephalopathy

Term	Definition
PMR	partial metabolic response
PPD	perpendicular diameter
PPK	population pharmacokinetics
PR	partial response (remission)
Q2W	once every 2 weeks
Q3W	once every 3 weeks
QoL	Quality of Life
RBC	red blood cell
RCC	renal cell carcinoma
RNA	ribonucleic acid
SAE	serious adverse event
SAP	Statistical Analysis Plan
SCT	stem cell transplant
SD	standard deviation
SDi	shortest diameter
SMD	stable metabolic disease
SmPC	Summary of Product Characteristics
t 1/2	Half life
T3	triiodothyronine
T4	thyroxine
TBili	total bilirubin
TIL	tumor-infiltrating lymphocyte
TSH	thyroid stimulating hormone
ULN	upper limit of normal
USPI	United States Package Insert
V	visit
V ss	volume of distribution at steady state
W	week

Term	Definition
WBC	white blood cell
WHO	World Health Organization
WOCBP	women of childbearing potential
[REDACTED]	

